5. STUDY PROCEDURES

5.1 Diagram of Procedures

Figure 3 shows a high-level sequence of study procedures that will be conducted in this study.

[figure not shown]

Figure 3 – Diagram of study procedures.

5.2 Subject Preparation

Study staff will confirm that the subject is eligible and willing to comply with applicable site requirements prior to starting study procedures. Demographic information, clinical history data, and pregnancy/menopausal status will be collected prior to the mammography exam.

No preparation for the breast imaging exam beyond that usually required by the investigational site is needed before procedures. After consenting, however, the study staff will show the subjects how to use the PAC mode prior to starting the exam.

5.3 Description of Study Procedures

5.3.1 Image acquisitions

Each subject will undergo her regularly scheduled breast imaging exam per standard practices at the investigational site, with the exception of the study-specific image acquisitions using PAC. The site uses combo mode (2D and 3D imaging) for screening mammography, and does not decompress between 3D and 2D imaging for a given view. Additionally, 3D acquisitions are conducted first per standard of practice. Thus, the sequence of imaging procedures will be conducted for the breast of interest, as shown in Figure 4. There shall be no repeat imaging administered using PAC mode, and standard of care will be used for imaging of the subject's other breast.

[figure not shown]

Figure 4 – Sequence of imaging procedures for the breast of interest (dark boxes = PAC, study-specific imaging, white boxes = standard of care (SoC) at the site).

A minimum of three (3) site technologists will perform the image acquisitions and related study procedures. Study procedures shall not impact the order in which the left and right breasts are imaged during the subjects' exams.

There will be two (2) study-specific image sets of the breast of interest for each subject. Image sets will consist of CC and MLO views obtained using PAC and CC and MLO views obtained using TC compression.

5.3.2 Image attribute review

Following acquisition, study-specific 3D images will be de-identified, and the time stamp, compression force, and breast thickness will be removed from the DICOM header to ensure the readers are blinded to the compression mode used for each image set. The image sets will be randomized for presentation during the image attribute reviews.

The 3D PAC and TC compression image sets will be evaluated by two (2) MQSA-qualified readers, with a third reader to provide adjudication if disagreement is observed between the two (2) readers' evaluations of "overall clinical image quality" (i.e. item number 9 in Section 5.3.2 Image attribute review). Images will be displayed on site-provided mammography review workstations/systems per the previously defined randomization scheme. Each reader will evaluate each image set independently from other reader(s) and have the freedom to navigate between views, as he/she would do in clinical practice.

In addition to the images, the following case data will be available to the readers for each image set during image attribute review:

- Techniques (anode, filter, kVp, mAs, half-value layer)
- Estimated average glandular dose per view (mGy)

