Procedures/Methods:	
The study population will consist of adult asymptomatic women presenting for screening 2D mammography. One breast of each subject will be identified as the “breast of interest,” which will undergo study-specific 3D imaging consisting of two-view (craniocaudal and mediolateral oblique) PA compression and image acquisition, followed by two-view technologist-controlled (TC) compression and image acquisition. The breast of interest will be randomly assigned to either the first breast imaged during the exam or the second breast imaged. TC compression and imaging, and procedures performed on the subject’s other breast will be conducted per standard of care.
 
Following image acquisition, 3D image quality evaluation will be conducted by MQSA-qualified readers. Prior to the reading session, images will be de-identified and the following information will be removed from the DICOM header to blind readers to the compression mode used during acquisition: time stamp, compression force, and breast thickness. The image sets will also be randomized for presentation during the image attribute reviews. Two (2) readers will evaluate each PAC and TC compression image set collected from each subject’s breast of interest and assess the acceptability of image attributes, as defined in the Guidance for Industry and FDA Staff - Class II Special Controls Guidance Document: Full-Field Digital Mammography System (2012). A third reader will provide adjudication, if there is disagreement for a given image set’s overall clinical image quality.
 
Workflow data, including the incidence of technologist intervention during acquisition and need for repeat image acquisition, will also be collected.
 
The proportion of PAC image sets that are of equal or higher acceptability than TC image sets will be calculated. A 95% confidence interval will be calculated using asymptotic method with continuity correction. The proportion of image sets indicated for repeated

	
image acquisition when using PA mode or TC mode will be summarized. Other endpoint data will be summarized using descriptive statistics. No statistical hypothesis is being tested in this study.

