1.2 Controls and Minimization of Bias

Due to the inherent difference in utility of standard and PAC modes, study subjects and study staff will not be blinded to the compression mode. However, the following bias control methods will be employed in this study:

- Selection bias will be limited by consecutively enrolling eligible subjects.
- Spectrum bias will be limited by using a population expected to represent the general population at the investigational site, without regard to race or ethnicity.
- PAC will be randomly assigned to either the first or second breast imaged to mitigate subject-learning bias associated with the amount of compression required for image acquisition.
- Reading order bias will be limited by randomizing the order of image set presentation to the readers.
- Readers conducting image quality evaluations will be blinded to the compression mode used to obtain the images.
- A minimum of three (3) radiology technologists will conduct the study procedures to mitigate bias introduced by technologist-specific practices.

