6.2 Image Attribute Review Data

Following training (see Section 7. Qualification and Training Plan), readers will evaluate all image sets from all cases by classifying each of the following image attributes as either “Acceptable” or “Not Acceptable” on CRFs.

- 1) Breast positioning, assessing coverage of the breast on craniocaudal and mediolateral oblique view, separately
- 2) Exposure, assessing visualization of the adipose and fibroglandular tissues, and visualization of breast tissue underlying the pectoralis muscle, separately
- 3) Breast compression, assessing overlapping breast structures, uniformity of exposure of fibroglandular tissues, adequacy of penetration of thicker portions of the breast, and exposure of thinner areas
 - a. If you answered “not acceptable,” was breast compression acceptable or not? If not, would you request repeat imaging in standard clinical practice? Yes or No.
 - b. If you answered “not acceptable,” was there another reason it was unacceptable? If not, would you request repeat imaging in standard clinical practice? Yes or No.
- 4) Sharpness due to motion
 - a. If you answered “not acceptable,” would you request repeat imaging in standard clinical practice? Yes or No.
- 5) Image contrast for differentiation of subtle tissue density differences
- 6) Sharpness, assessing the edges of fine linear structures, tissue borders, and benign calcifications
- 7) Tissue visibility at the skin line
- 8) Noise, i.e., noise obscuring breast structures or suggestive of structures not actually present
- 9) Artifacts due to image processing, detector failure and other factors external to the breast on hard-copy and soft-copy displays
- 10) Overall clinical image quality
 - a. If you answered “not acceptable” for overall clinical image quality, would you request repeat imaging in standard clinical practice? Yes or No.
 - b. If yes, which view would you request for repeat imaging? CC only, MLO only, or both CC and MLO?

If an issue is encountered by any reader during the image attribute review of any image set, an explanation of the issue will be documented on a CRF by the reader.

Readers will also classify the breast density of each image set as follows:

- 1) Almost entirely fatty
- 2) Scattered areas of fibroglandular density
- 3) Heterogeneously dense
- 4) Extremely dense

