10.3.2 Analysis of Primary Endpoint

The proportion of PAC image sets that are of equal or higher acceptability than TC image sets will be calculated. A 95% confidence interval will be calculated using asymptotic method with continuity correction. This analysis will also be performed for subgroups defined by the randomized breast of interest (i.e. breast of interest imaged first versus breast of interest imaged second).

Proportion of images with acceptable overall image quality will be summarized for PAC image sets and TC image sets separately, with 95% confidence interval using asymptotic method with continuity correction.

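### No separation is stated between a reader's PAC and TC readings of the same breast, and a rating carried over from one to the other can only favour PAC on the primary statistic

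*Combined protocol and SAP*

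**What the plan says.** Each subject contributes a matched pair: "There will be two (2) study-specific image sets of the breast of interest for each subject" (5.3.1), one acquired with PAC and one with TC compression.

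The same people read both members of the pair. The synopsis (Procedures/Methods) says "Two (2) readers will evaluate each PAC and TC compression image set", and 6.2 says "readers will evaluate all image sets from all cases". At the target of 30 subjects, that is 60 sets per reader.

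Order is controlled by randomisation alone. Section 1.2 says "Reading order bias will be limited by randomizing the order of image set presentation to the readers", and 5.3.2 says "The image sets will be randomized for presentation during the image attribute reviews". Section 5.3.2 adds that display is "per the previously defined randomization scheme", but no section describes that scheme. The synopsis mentions one session ("Prior to the reading session, images will be de-identified") and gives no interval.

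Section 5.3.2 requires each reader to work independently of the other readers. It does not address independence between one reader's two ratings of the same breast. It strips time stamp, force and thickness from the header, but shows readers kVp, mAs and average glandular dose.

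The rating is binary (3.2.1), and the primary analysis (10.3.2) is: "The proportion of PAC image sets that are of equal or higher acceptability than TC image sets will be calculated". The proportion acceptable is also reported for each mode separately.

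**The concern.** The two sets show the same breast in the same views from the same visit, and removing header fields does not hide that. A reader who meets the second set soon after the first may recognise it and repeat the earlier rating.

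On many endpoints this would only blunt the comparison. Here ties count for PAC, so repeated ratings move the result one way. The gain equals the share of pairs copied times the true rate of PAC-worse pairs, so it is largest when PAC really is worse, which is the finding the study most needs to be able to show. No hypothesis or success threshold is set (10.1), so the estimate and its interval are the main evidence going into a regulatory submission.

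A second, smaller issue is blinding. Two sets of one breast seen close together are easier to compare on the displayed kVp, mAs and dose than two sets seen weeks apart.

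**Working it through.** **Scale: the plan's own precision figure.** The plan gives no figure for reading order. For the primary proportion, 10.2 states a 95% interval no wider than 13% at 95% with n = 30. Wald: 0.95 ± 1.96 × √(0.95 × 0.05/30) = 0.95 ± 0.078. Cut at 1, this is 0.872 to 1.000, width 12.8%, so the figure reproduces without a continuity correction. (With the correction named in 10.3.2, ± 1/60, the width is 14.5%; that is a separate matter.) One subject is 1/30 = 3.3 percentage points.

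**Direction.** Write the final ratings as PAC/TC, A for acceptable and U for unacceptable. A/A, A/U and U/U count as success; only U/A is failure. Copying turns a pair into A/A or U/U. A U/A pair therefore moves from failure to success, and an A/U pair that becomes a tie remains a success. No pair moves the other way.

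**How close pairs fall.** Assumption: all 60 sets are shuffled together without restriction.

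Expected pairs within d positions = 30 × Σ(k = 1 to d) 2(60 − k)/(60 × 59).

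- d = 1: 30 × 2 × 59/3540 = 1.00
- d = 5: 30 × 2 × 285/3540 = 4.83, which is 16% of 30
- d = 10: 30 × 2 × 545/3540 = 9.24, which is 31% of 30

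The chance of at least one adjacent pair, by inclusion-exclusion, is 63.5%; 200,000 simulated orders gave 63.4%.

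**Effect on the primary, assumed upper scenario.** Assumptions, none from the documents: every pair within five (or ten) positions is copied; PAC and TC ratings are otherwise independent; there is one final rating per set; acceptability rates are as shown.

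Primary = 1 − (1 − r)(1 − p_PAC) p_TC, where r is the share of pairs copied.

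| PAC / TC acceptable | r = 0 | r = 0.161 | r = 0.308 | Gain in subjects of 30 |
|---|---|---|---|---|
| 95% / 97% | 95.2% | 95.9% | 96.6% | 0.23 to 0.45 |
| 90% / 97% | 90.3% | 91.9% | 93.3% | 0.47 to 0.90 |

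The gain is 30 × r × (1 − p_PAC) × p_TC; for example 30 × 0.308 × 0.10 × 0.97 = 0.90.

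**Relaxing two assumptions.**

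- *Correlated ratings.* With maximal positive correlation at 95%/97%, PAC-worse pairs fall to 97% − 95% = 2%. The primary then moves from 98.0% to 1 − 0.839 × 0.02 = 98.3% or 1 − 0.692 × 0.02 = 98.6%.
- *Different orders for the two readers.* If the orders are independent, a pair is close for both readers in only 30 × 0.161² = 0.8 subjects (within five) or 30 × 0.308² = 2.8 (within ten).

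**The case against.** Three objections carry weight.

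First, a reader might infer that the protocol prescribes an unrestricted shuffle of all 60 sets. It does not say so. The scheme mentioned in 5.3.2 may contain restrictions or may simply refer back to the preceding paragraph. What can be said is that no separation rule is stated. The positional figures depend on the shuffle assumption; ordering at random only within subject is not excluded either, and would put the two sets of every subject together.

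Second, a reader might infer that recall will inflate the result. The documents contain nothing from which a copying rate could be estimated, and close viewing could instead sharpen contrasts and produce fewer ties. The one-way direction is a property of copying under this endpoint, not of every effect of recognition.

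Third, the effect is modest. Even the upper scenario stays below one subject, against a planned interval width of 13 points, and no formal decision depends on it. Correlated ratings and different reader orders reduce it further. With two readers and an adjudicator, one reader's copied rating also does not fix the final rating by itself.

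Two partial protections deserve mention. The separate PAC and TC proportions give a view that the tie rule does not affect, although copying draws them together too. On blinding, the displayed technique and dose values are a possible cue in any order; separating the sets makes direct comparison harder but does not remove the cue.

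These points limit the size and certainty of the concern. They do not supply the missing separation.

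**Conclusion.** The concern holds as a design weakness that should be corrected before reading starts. The stated control, random order, does not keep a reader's two ratings of one breast apart, and the endpoint turns any copied rating into a result no worse for PAC.

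The direction under copying follows from the endpoint definition. The size does not come from the documents: the gain of 0.23 to 0.90 subject of 30 assumes an unrestricted shuffle, full copying within five or ten positions, independent ratings and one rating per set, and is best read as an upper scenario.

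The documents do not support a claim that the primary result will be materially biased or that the blinding fails. The case for change rests on a known direction, a clearly better reading design and a low cost.

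**What to change.** In 5.3.2, replace simple randomisation with restricted randomisation and describe the scheme there:

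- Each reader reads in two sessions, separated by an interval fixed in the protocol before reading starts. At least two weeks is one example; that figure is an assumption, for the sponsor to set.
- Each subject contributes one set to each session. The PAC set comes first for half the subjects and the TC set first for the other half.
- Order is random within each session.
- The adjudicator does not see both sets of one subject in the same sitting.

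If a separate reading plan already contains such a rule, stating it in 5.3.2 is enough.

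Readers, number of reads and sample size do not change. The cost is one extra sitting per reader and a short delay. The study is expected to last about three months but gives no reading timeline, so the sponsor should check that the chosen interval fits.

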1. BACKGROUND AND JUSTIFICATION

1.1 Screening Mammography and Patient-Assisted Compression

Leading authorities on breast cancer recommend regular screening mammography for women aged 40 years and older as a means of early detection for breast cancer, leading to increased survival rates and more treatment options.^{2, 3, 4} Numerous randomized trials have demonstrated that regular mammographic screening reduces breast cancer mortality,^{5, 6, 7, 8, 9} with more than 40% reduction in breast cancer deaths.^{10, 11} Amidst the success of screening mammography, clinicians struggle to maintain patient participation in regular screening programs. Notably, a systematic review by Whelehan, et al. concluded that pain experienced during screening mammography (e.g. compression pain) contributed to reduced rates of repeat participation in regular screening programs.¹²

Adequate breast compression during mammography creates uniform thickness and flattens tissues,⁴ which is necessary to obtain sufficient image quality^{4, 13, 14} and reduce radiation dose.^{4, 15} Various methods are being investigated to maintain sufficient compression while reducing pain/discomfort associated with mammography. Specifically, studies have shown that a personalized approach to compression can significantly reduce pain intensity and discomfort experienced by patients while maintaining diagnostic image quality.^{16, 17, 18}

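### Section 5.3.2 hides compression force and breast thickness from the readers but shows them glandular dose, mAs and kVp while they score: a possible and avoidable cue to compression mode

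*Combined protocol and SAP*

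**What the plan says.** Section 5.3.2 states the blinding step and its purpose: "time stamp, compression force, and breast thickness will be removed from the DICOM header to ensure the readers are blinded to the compression mode". The synopsis (Procedures/Methods) lists the same three items, "removed from the DICOM header to blind readers to the compression mode used during acquisition: time stamp, compression force, and breast thickness". Section 1.2 counts reader blinding among the bias controls.

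Section 5.3.2 then says that further "case data will be available to the readers for each image set during image attribute review". The two entries are "Techniques (anode, filter, kVp, mAs, half-value layer" and "Estimated average glandular dose per view (mGy". The synopsis does not mention this display. No passage gives a reason for it, and nothing in the text excludes the third, adjudicating reader.

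Three other statements bear on the point:
- Section 1.1 says adequate compression is needed to obtain sufficient image quality "and reduce radiation dose".
- Section 1.2 says "study subjects and study staff will not be blinded to the compression mode".
- On reading order, 5.3.2 says: "The image sets will be randomized for presentation during the image attribute reviews". It refers to a scheme defined beforehand but gives no details, and no passage says that the two sets of one breast are kept apart.

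**The concern.** The plan removes force and thickness because they could reveal the mode. Dose is a quantity that the plan itself ties to compression, and it is left on view. mAs and kVp belong with it by inference, as exposure settings; section 1.1 does not name them.

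The primary endpoint is a reader's acceptable/unacceptable judgement of overall image quality. Subjects and staff know the mode, so only the reader blind keeps expectations about PAC out of that judgement. Two independent readers with adjudication do not clearly remove a cue that all of them can see. If a reader inferred the mode and let that affect a rating, the reported proportion of PAC sets rated equal to or better than TC could shift in either direction.

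**Working it through.** The plan gives no figure on this point. Its one precision statement, the interval width in 10.2, is unaffected. The check is therefore a comparison of passages, followed by an illustration.

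**Passages side by side**
- Removed (5.3.2, synopsis): time stamp, compression force, breast thickness.
- Shown during scoring (5.3.2): AGD per view, kVp, mAs, anode, filter, half-value layer.
- Link to compression (1.1): stated for dose, inferred for mAs and kVp. None is stated for anode, filter or half-value layer.
- Expected PAC/TC difference in dose: not given. Dose in both modes is an exploratory endpoint (3.2.3).

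The cue is possible on the plan's own reasoning, but the documents do not allow it to be sized.

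**Illustration; every input is assumed**

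Let log dose be normal, with SD between breasts *sb* = 0.2 to 0.4, SD within a breast *sw* = 0.05 to 0.10, and mode shift *d* = ln(1 + shift). The best accuracy in guessing mode from dose alone is:
- set seen alone: Φ(*d* / (2√(*sb*² + *sw*²)))
- two sets recognised as the same breast, with the direction of the shift known: Φ(*d* / (√2 · *sw*))

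For a 5% shift, *d* = 0.0488:
- alone, *sb* 0.4 and *sw* 0.10: 0.0488 / (2 × 0.412) = 0.059, Φ = 0.524
- alone, *sb* 0.2 and *sw* 0.05: 0.0488 / (2 × 0.206) = 0.118, Φ = 0.547
- pair, *sw* 0.10: 0.0488 / 0.1414 = 0.345, Φ = 0.635
- pair, *sw* 0.05: 0.0488 / 0.0707 = 0.690, Φ = 0.755

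| Assumed dose shift | *d* | Set seen alone | Recognised pair, direction known |
|---|---|---|---|
| 0% | 0 | 50% | 50% |
| 5% | 0.0488 | 52.4–54.7% | 63.5–75.5% |
| 10% | 0.0953 | 54.6–59.1% | 75.0–91.1% |

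**How often the two sets of one breast would fall close together**

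Assume an unrestricted random order of the 60 sets. There are 60 × 59 / 2 = 1,770 pairs of positions, of which 59 are adjacent. The expected number of adjacent same-breast pairs is 30 × 59 / 1,770 = 1. Pairs of positions at most five apart number 59 + 58 + 57 + 56 + 55 = 285, giving 30 × 285 / 1,770 = 4.8 of the 30 breasts.

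**One step in the endpoint**

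A pair counts against PAC only when PAC is unacceptable and TC acceptable (10.3.2). With 30 pairs, one changed final rating moves the proportion by 0 or 1/30 = 3.3 points, whatever the cause. This is the size of one step and does not measure the leak.

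**The case against.** The strongest reply is that bias needs four things, none of which the documents show directly: a systematic PAC/TC dose difference, a reader who notices it, a correct inference about mode, and a binary rating changed because of it. Section 1.1 speaks of adequate compression in general and does not compare PAC with TC. Under PAC the operator starts the compression (2.1) and the technologist may intervene (6.1), so doses may barely differ. Readers already rate compression from the image (6.2, item 3), so dose adds only an increment. Exposure, contrast and noise are also rated, and the Guidance may expect technique data for that; this cannot be checked here. No hypothesis is tested (10.1), so no decision rule is at risk.

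All of this stands, and it limits the size of the point. It does not explain why a quantity tied to compression is shown when force and thickness are hidden. Randomised presentation does not remove the cue.

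A reader might infer from the last column of the table that mode could be identified in most pairs. The documents do not support that. Sets are de-identified and scored one at a time in randomised order. Side-by-side reading is not described; the freedom to navigate is between views. The pair figures also require recognition of the same breast, knowledge of which mode gives the higher dose, and a shift that nobody has documented. Separation of the two sets is unstated, which is not the same as absent.

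**Conclusion.** The point holds as a minor gap in the blinding procedure. Dose, and by inference mAs and kVp, is a possible and avoidable cue to mode in the only blind that protects the subjective primary endpoint.

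Its effect cannot be sized from the documents and may be nil; the direction is unknown. The guessing accuracies rest wholly on assumed shifts and SDs, and they describe guessing the mode, not any change in ratings. A reader might go further and conclude that the blind fails, that the primary result is biased for or against PAC, or that every displayed technique factor reveals the mode. The documents support none of these: they report no dose difference between modes and do not link anode, filter or half-value layer to mode. That the cue is avoidable is also a judgement, resting on the absence of any stated need for these data in scoring.

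**What to change.** In 5.3.2 and the synopsis, add AGD, mAs and kVp to the items removed from the header of the reading copy. Replace the display in 5.3.2 with a statement that these values are withheld from all readers, including the adjudicator, until that reader's scores are locked. Keep them on the acquisition CRF (6.1), so that the dose summary in 10.3.3 is unaffected. Anode, filter and half-value layer can be handled the same way for simplicity; no analysis in 10.3 names them.

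If the sponsor holds that attribute scoring requires these data, state that reason in 5.3.2 and specify that the two sets of one breast are kept apart in the reading order.

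The cost is a longer removal list in two places and a score-lock step. Force and thickness are already captured for the CRF and stripped for reading, so the same handling can be extended. Sample size and analyses do not change. The downside is that readers would rate exposure, contrast and noise from the image alone.
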